### **10.2. Patient Consent**

The informed consent/assent documents and any patient recruitment materials must be in compliance with local regulatory requirements and legal requirements, including applicable privacy laws.

The informed consent/assent documents used during the informed consent process and any patient recruitment materials must be reviewed and approved by Pfizer, approved by the institutional review board (IRB)/independent ethics committee (IEC) before use, and available for inspection.

The investigator must ensure that each study patient, or his/her legally acceptable representative, is fully informed about the nature and objectives of the study, the sharing of data relating to the study and possible risks associated with participation, including the risks associated with the processing of the patient's personal data. The investigator further must ensure that each study patient, or his or her legally acceptable representative, is fully informed about his or her right to access and correct his or her personal data and to withdraw consent for the processing of his or her personal data.

Whenever consent is obtained from a patient's legally acceptable representative, the patient's assent (affirmative agreement) must subsequently be obtained when the patient has the capacity to provide assent, as determined by the IRB/IEC. If the investigator determines that a patient's decisional capacity is so limited that he or she cannot reasonably be consulted, then, as permitted by the IRB/IEC and consistent with local regulatory and legal requirements, the patient's assent may be waived with source documentation of the reason assent was not obtained. If the study patient does not provide his or her own consent, the source documents must record why the patient did not provide consent (eg, minor, decisionally impaired adult), how the investigator determined that the person signing the consent was the patient's legally acceptable representative, the consent signer's relationship to the study patient (eg, parent, spouse), and that the patient's assent was obtained or waived. If assent is obtained verbally, it must be documented in the source documents.

The investigator, or a person designated by the investigator, will obtain written informed consent from each patient or the patient's legally acceptable representative before any study-specific activity is performed. The investigator will retain the original of each patient's signed consent/assent document.

#### **10.2.1. Participation in Investigational Clinical Trials**

If a patient in Spain elects to participate in a double-blind or open-label interventional trial, entry of data into THAOS will be prohibited from the date patient begins taking study drug (or device) until the end of the interventional trial. Data collected prior to a patient receiving treatment in a double-blind or open-label interventional trial (eg, baseline, pre-treatment assessments, or any historical data) can be entered into the THAOS electronic data record/database and data collection can resume after completion of the interventional trial. Data collected during the time of participation in an interventional trial may not be entered into THAOS

For patients enrolled outside of Spain, if a patient elects to participate in a double-blind investigational clinical trial, collection of THAOS data will be temporarily suspended during the period that the patient is taking study drug (or device).

Data collected prior to a patient receiving treatment in a double-blind investigational trial (eg, baseline, pre-treatment assessments, or any historical data), as well as data collected after the patient's completion or withdrawal from a double-blind investigational trial, can be entered into the THAOS electronic data record/database. Data collected during the course of the clinical trial may be entered retrospectively at the end of the trial if the THAOS principal investigator obtains and documents approval from the study sponsor who conducted the clinical trial. Retrospective data entry cannot occur until the study has been unblinded,

which will permit identification of the treatment received during the trial. No reconciliation between databases will occur.

As the goal of the survey is to document the course (or natural history) of TTR amyloidosis, the use of known interventions, including open-label investigational agents or devices, will be permitted. For interventional clinical trials that include open-label tafamidis or other open-label investigational products, patients may continue in THAOS, with the approval of the Sponsor, but AE data collection will be addressed through the interventional clinical trial sponsor. The THAOS principal investigator is responsible for obtaining and documenting approval from the study sponsor for investigational agents other than tafamidis.

### **10.3. Patient Withdrawal**

Patients may withdraw from the study at any time at their own request, or they may be withdrawn at any time at the discretion of the investigator or sponsor for safety, behavioral, or administrative reasons. In any circumstance, every effort should be made to document patient outcome, if applicable. The investigator would inquire about the reason for withdrawal and follow-up with the patient regarding any unresolved AEs.

Whenever possible, the patient should return for a final visit and the reason for withdrawal recorded. If a patient does not return for further assessments and no longer wishes to participate in THAOS, the reason the patient provides for discontinuation from the survey will be recorded. In the event that a patient does not complete an annual visit, can no longer be contacted within one year of a scheduled annual visit, and the patient's status is unknown, the patient will be considered lost to follow-up and the principal investigator (PI) will be required to change the patient status in that individual's THAOS clinical database accordingly.

If the patient withdraws from the study and also withdraws consent for disclosure of future information, no further evaluations should be performed, and no additional data should be collected. The sponsor may retain and continue to use any data collected before such withdrawal of consent.

### **10.4. Institutional Review Board (IRB)/Independent Ethics Committee (IEC)**

It is the responsibility of the investigator to have prospective approval of the study protocol, protocol amendments, and informed consent forms, and other relevant documents, (eg, recruitment advertisements), if applicable, from the IRB/IEC. All correspondence with the IRB/IEC should be retained by the investigator. Copies of IRB/IEC approvals should be forwarded to Pfizer.

### **10.5. Ethical Conduct of the Study**

The study will be conducted in accordance with legal and regulatory requirements, as well as with scientific purpose, value and rigor and follow generally accepted research practices described in Guidelines for Good Pharmacoepidemiology Practices (GPP) issued by the International Society for Pharmacoepidemiology (ISPE), Good Practices for Outcomes Research issued by the International Society for Pharmacoeconomics and Outcomes Research (ISPOR), International Ethical Guidelines for Epidemiological Research issued by the Council for International Organizations of Medical Sciences (CIOMS), EMA European

Network of Centres for Pharmacoepidemiology and Pharmacovigilance (ENCePP) Guide on Methodological Standards in Pharmacoepidemiology, and Food and Drug Administration (FDA) Guidance for Industry: Good Pharmacovigilance and Pharmacoepidemiologic Assessment, FDA Guidance for Industry and FDA Staff: Best Practices for Conducting and Reporting of Pharmacoepidemiologic Safety Studies Using Electronic Healthcare Data, Guidance for Industry: Patient-Reported Outcome Measures: Use in Medical Product Development to Support Labeling Claims.

## 11. MANAGEMENT AND REPORTING OF ADVERSE EVENTS/ADVERSE REACTIONS FOR TAFAMIDIS-TREATED SUBJECTS

### 11.1. Requirements

The table below summarizes the requirements for recording safety events in the THAOS electronic data record and for reporting safety events on the non-interventional study (NIS) adverse event monitoring (AEM) Report Form to Pfizer Safety. These requirements are delineated for 3 types of events: (1) serious adverse events (SAEs); (2) non-serious AEs (as applicable); and (3) scenarios involving drug exposure, including exposure during pregnancy (EDP), exposure during breast feeding, medication error, overdose, misuse, extravasation, and occupational exposure. These events are defined in the section “[Definitions of Safety Events](#)”

Safety event	Recorded in the THAOS electronic data record	Reported on the NIS AEM Report Form to Pfizer Safety within 24 hours of awareness
SAE	All	All
Non-serious AE	All	None
Scenarios involving exposure to a drug under study, including EDP, exposure during breastfeeding, medication error, overdose, misuse, extravasation; lack of efficacy; and occupational exposure	All (regardless of whether associated with an AE), except occupational exposure	All (regardless of whether associated with an AE)

For each AE, the investigator must pursue and obtain information adequate both to determine the outcome of the AE and to assess whether it meets the criteria for classification as a SAE (see section “[Serious Adverse Events](#)” below).

Safety events listed in the table above must be reported to Pfizer within 24 hours of awareness of the event by the investigator **regardless of whether the event is determined by the investigator to be related to tafamidis**. In particular if the SAE is fatal or life-threatening, notification to Pfizer or its designated representative must be made

immediately, irrespective of the extent of available event information. This timeframe also applies to additional new (follow-up) information on previously forwarded safety event reports. In the rare situation that the investigator does not become immediately aware of the occurrence of a safety event, the investigator must report the event within 24 hours after learning of it and document the time of his/her first awareness of the events.

For safety events that are considered serious, or that are identified in the far-right column of the table above, that are reportable to Pfizer within 24 hours of awareness, the investigator is obligated to pursue and to provide any additional information to Pfizer in accordance with this 24-hour timeframe. In addition, an investigator may be requested by Pfizer to obtain specific follow-up information in an expedited fashion. This information is more detailed than that recorded in the THAOS electronic clinical database. In general, this will include a description of the AE in sufficient detail to allow for a complete medical assessment of the case and independent determination of possible causality. Any information relevant to the event, such as concomitant medications and illnesses must be provided. In the case of a patient death, a summary of available autopsy findings must be submitted as soon as possible to Pfizer or its designated representative.

## **11.2. Reporting Period**

For each patient, the safety event reporting period begins at the time of the patient's first dose of tafamidis or the time of the patient's informed consent if s/he is being treated with tafamidis at study start and lasts through the end of the observation period of the study, which must include at least 28 calendar days following the last administration of a drug under study; a report must be submitted to Pfizer Safety (or its designated representative) for any of the types of safety events listed in the table above occurring during this period.

If a patient was administered a drug under study on the last day of the observation period, then the reporting period should be extended for 28 calendar days following the end of observation.

Most often, the date of informed consent is the same as the date of enrollment. In some situations, there may be a lag between the dates of informed consent and enrollment. In these instances, if a patient provides informed consent but is never enrolled in the study (eg, patient changes his/her mind about participation), the reporting period ends on the date of the decision to not enroll the patient.

If the investigator becomes aware of a SAE occurring at any time after completion of the study and s/he considers the SAE to be related to tafamidis, the SAE also must be reported to Pfizer Safety.

### **11.3. Causality Assessment**

The investigator is required to assess and record the causal relationship.

For all AEs, sufficient information should be obtained by the investigator to determine the causality of each AE. For AEs with a causal relationship to tafamidis, follow-up by the investigator is required until the event and/or its sequelae resolve or stabilize at a level acceptable to the investigator, and Pfizer concurs with that assessment.

An investigator's causality assessment is the determination of whether there exists a reasonable possibility that tafamidis caused or contributed to an AE. If the investigator's final determination of causality is "unknown" and the investigator cannot determine whether tafamidis caused the event, then the event will be handled as related to tafamidis for reporting purposes and the safety event must be reported within 24 hours.

If the investigator cannot determine the etiology of the event but the investigator determines that tafamidis did not cause the event, this should be clearly documented in the THAOS electronic clinical database and the NIS AEM Report Form.

### **11.4. Definitions of Safety Events**

#### **11.4.1. Adverse Events**

An AE is any untoward medical occurrence in a patient administered a medicinal product. The event need not necessarily have a causal relationship with the product treatment or usage. Examples of AEs include but are not limited to:

- Abnormal test findings (see below for circumstances in which an abnormal test finding constitutes an AE);
- Clinically significant symptoms and signs;
- Changes in physical examination findings;
- Hypersensitivity;
- Progression/worsening of underlying disease;
- Lack of efficacy;
- Drug abuse;
- Drug dependency.

Additionally, for medicinal products, they may include the signs or symptoms resulting from:

- Drug overdose;
- Drug withdrawal;

- Drug misuse;
- Off-label use;
- Drug interactions;
- Extravasation;
- EDP;
- Exposure during breast feeding;
- Medication error;
- Occupational exposure.

#### **11.4.2. Abnormal Test Findings**

The criteria for determining whether an abnormal objective test finding should be reported as an AE are as follows:

- Test result is associated with accompanying symptoms, and/or
- Test result requires additional diagnostic testing or medical/surgical intervention, and/or
- Test result leads to a change in study dosing or discontinuation from the study, significant additional concomitant drug treatment, or other therapy, and/or
- Test result is considered to be an AE by the investigator or sponsor.

Merely repeating an abnormal test, in the absence of any of the above conditions, does not constitute an AE. Any abnormal test result that is determined to be an error does not require reporting as an AE.

#### **11.4.3. Serious Adverse Events**

A SAE is any untoward medical occurrence in a patient administered a medicinal or nutritional product (including pediatric formulas) at any dose that:

- Results in death;
- Is life-threatening (immediate risk of death);
- Requires inpatient hospitalization or prolongation of hospitalization (see below for circumstances that do not constitute AEs);

- Results in persistent or significant disability/incapacity (substantial disruption of the ability to conduct normal life functions);
- Results in congenital anomaly/birth defect.

Medical and scientific judgment is exercised in determining whether an event is an important medical event. An important medical event may not be immediately life-threatening and/or result in death or hospitalization. However, if it is determined that the event may jeopardize the subject or may require intervention to prevent one of the other AE outcomes listed in the definition above, the important medical event should be reported as serious.

Examples of such events are intensive treatment in an emergency room or at home for allergic bronchospasm; blood dyscrasias or convulsions that do not result in hospitalization; or development of drug dependency or drug abuse.

Additionally, any suspected transmission via a Pfizer product of an infectious agent, pathogenic or non-pathogenic, is considered serious. The event may be suspected from clinical symptoms or laboratory findings indicating an infection in a patient exposed to a Pfizer product. The terms “suspected transmission” and “transmission” are considered synonymous. These cases are considered unexpected and handled as serious expedited cases by pharmacovigilance personnel. Such cases are also considered for reporting as product defects, if appropriate.

### **11.5. Hospitalization**

Hospitalization is defined as any initial admission (even if less than 24 hours) to a hospital or equivalent healthcare facility or any prolongation to an existing admission. Admission also includes transfer within the hospital to an acute/intensive care unit (eg, from the psychiatric wing to a medical floor, medical floor to a coronary care unit, neurological floor to a tuberculosis unit). An emergency room visit does not necessarily constitute a hospitalization; however, an event leading to an emergency room visit should be assessed for medical importance.

Hospitalization in the absence of a medical AE is not in itself an AE and is not reportable. For example, the following reports of hospitalization without a medical AE are not to be reported:

- Social admission (eg, patient/subject has no place to sleep);
- Administrative admission (eg, for yearly exam);
- Optional admission not associated with a precipitating medical AE (eg, for elective cosmetic surgery);
- Hospitalization for observation without a medical AE;

- Admission for treatment of a pre-existing condition not associated with the development of a new AE or with a worsening of the pre-existing condition (eg, for work-up of persistent pre-treatment lab abnormality);
- Protocol-specified admission during clinical study (eg, for a procedure required by the study protocol).

## **11.6. Scenarios Necessitating Reporting to Pfizer Safety within 24 Hours**

Scenarios involving exposure during pregnancy, exposure during breastfeeding, medication error, overdose, misuse, extravasation, lack of efficacy, and occupational exposure are described below.

### **11.6.1. Exposure During Pregnancy**

1. An exposure during pregnancy (EDP) occurs if a female becomes, or is found to be, pregnant either while receiving or having been directly exposed to (eg, environmental exposure) tafamidis, or the female becomes, or is found to be, pregnant after discontinuing and/or being directly exposed to tafamidis (maternal exposure).
2. An example of environmental exposure would be a case involving direct contact with a Pfizer product in a pregnant woman (eg, a nurse reports that she is pregnant and has been exposed to chemotherapeutic products).

As a general rule, prospective and retrospective EDP reports from any source are reportable irrespective of the presence of an associated AE and the procedures for SAE reporting should be followed.

If a study participant becomes, or is found to be, pregnant during the study participant's treatment with tafamidis, this information must be submitted to Pfizer, irrespective of whether an adverse event has occurred, using the NIS AEM Report Form and the EDP Supplemental Form, and through the Tafamidis Enhanced Surveillance for Pregnancy Outcomes (TESPO). Reporting to TESPO for women exposed to tafamidis will also include a 6-month and 12-month post-birth follow-up questionnaire regarding developmental milestones.

In addition, the information regarding environmental exposure to tafamidis in a pregnant woman (eg, a patient reports that she is pregnant and has been exposed to a cytotoxic product by inhalation or spillage) must be submitted using the NIS AEM Report Form and the EDP supplemental form. This must be done irrespective of whether an AE has occurred.

Information submitted should include the anticipated date of delivery (see below for information related to termination of pregnancy).

Follow-up is conducted to obtain general information on the pregnancy; in addition, follow-up is conducted to obtain information on EDP outcome for all EDP reports with pregnancy outcome unknown. A pregnancy is followed until completion or until pregnancy termination (eg, induced abortion) and Pfizer is notified of the outcome. This information is provided as a follow up to the initial EDP report.

In the case of a live birth, the structural integrity of the neonate can be assessed at the time of birth. In the event of a termination, the reason(s) for termination should be specified and, if clinically possible, the structural integrity of the terminated fetus should be assessed by gross visual inspection (unless pre-procedure test findings are conclusive for a congenital anomaly and the findings are reported).

If the outcome of the pregnancy meets the criteria for an SAE (eg, ectopic pregnancy, spontaneous abortion, intrauterine fetal demise, neonatal death, or congenital anomaly [in a live born, a terminated fetus, an intrauterine fetal demise, or a neonatal death]), the procedures for reporting SAEs should be followed.

Additional information about pregnancy outcomes that are reported as SAEs follows:

- Spontaneous abortion includes miscarriage and missed abortion;
- Neonatal deaths that occur within 1 month of birth should be reported, without regard to causality, as SAEs. In addition, infant deaths after 1 month should be reported as SAEs when the investigator assesses the infant death as related or possibly related to exposure to investigational product.

Additional information regarding the EDP may be requested. Further follow-up of birth outcomes will be handled on a case-by-case basis (eg, follow-up on preterm infants to identify developmental delays).

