### ATTR-PN

The hereditary forms of ATTR amyloidosis are autosomal dominantly inherited diseases with a variable penetrance that can affect multiple generations in a family and have a substantial impact on patients and their families. Val30Met (substitution of methionine for valine at position 30) is the most common mutation associated with ATTR-PN, with symptom onset usually in the third to fourth decade of life, depending on the mutation carried and the patient's ethnic background.

The main feature of ATTR-PN is progressive sensorimotor and autonomic neuropathy. Sensory neuropathy typically starts in the lower extremities followed by motor neuropathy within a few years. Autonomic neuropathy quite often accompanies the sensory and motor deficits. ATTR-PN is more frequently observed in certain areas of Portugal, Sweden, and Japan but has been identified throughout the world. Although penetrance varies greatly among geographic and ethnic foci, the outcome of the disease is invariably progressive and fatal. The lifespan for patients is severely shortened, with death occurring within a mean of 10-15 years from the first symptoms.

Disease-modifying therapies for ATTR-PN include TTR stabilizer tafamidis, orthotopic liver transplantation, RNA interference (RNAi)-based drugs, and transthyretin-directed antisense oligonucleotide drugs. Tafamidis meglumine was approved in the European Union (EU) on 16 November 2011 for the treatment of ATTR in adult patients with Stage 1 symptomatic polyneuropathy to delay peripheral neurologic impairment. Currently, it is approved for ATTR-PN in over 40 countries worldwide. Subsequently, Tegsedi (inotersen) and Onpattro (patisiran) for the treatment of hereditary ATTR amyloidosis in patients with polyneuropathy (ATTR-PN) have also been approved in the EU and US.

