## **9.5. Study Size**

THAOS has been open since 2007. There is no set number of patients who will be enrolled in the survey. Patients will be enrolled from different countries around the world. All patients who take part in this survey will be followed until the survey is declared complete by Pfizer (currently estimated to be the year 2023) or as long as they are able to participate, or until they withdraw consent to participate.

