### **4 HYPOTHESES AND DECISION RULES**

There are no hypotheses associated with this survey. All analyses will be descriptive.

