### Adverse Events & Serious Adverse Events

All adverse events will be coded according to the latest Medical Dictionary for Regulatory Activities (MedDRA) version at the time of analysis.

Adverse events (all causality and treatment-related) will be summarized by severity and starting dose using the tafamidis treated set by phenotype at enrollment and overall, CCI [REDACTED] and either predominantly cardiac or mixed phenotype at enrollment, tafamidis treated set for patients who had severe hepatic impairment at baseline, tafamidis treated set by liver transplantation status (liver transplant prior to first dose of tafamidis/liver transplant after the first dose of tafamidis/no liver transplant).

Separate summaries will be provided for all AEs, treatment related AEs, all SAEs, treatment related SAEs, AEs leading to dose reduction, AEs leading to withdrawal of tafamidis (temporarily or permanently, or delayed) and AEs leading to tafamidis dose interruptions.

Listings will be provided for adverse events corresponding to all enrolled patients and for patients with off-label usage of tafamidis. A separate listing of SAEs will also be provided for tafamidis treated set.

The following AE summary tables will be provided corresponding to some of the important potential risks using the tafamidis treated set.

- For **hepatotoxicity** using the search criteria: MedDRA SMQ (Standardized MedDRA Query) [Broad and narrow] Drug related hepatic disorders – comprehensive search. The derivations and conventions related to the search criteria will follow the programming specifications done in the Periodic Safety Update Report (PSUR) 12 for tafamidis.
- For **reproductive and developmental toxicity and lactation**:
  - MedDRA SMQ (Broad and narrow): Congenital, familial and genetic disorders; Foetal disorders; Neonatal disorders, Neonatal exposures via breast milk.
  - MedDRA Preferred terms (PTs): Exposure during pregnancy, Exposure via father, Foetal exposure during delivery, Foetal exposure during pregnancy, Foetal exposure timing unspecified, Maternal exposure before pregnancy, Maternal exposure during delivery, Maternal exposure during pregnancy, Maternal exposure timing unspecified, Drug exposure before

- pregnancy, Exposure via breastmilk, Maternal drug affecting foetus, Maternal exposure during breastfeeding
- The derivations and conventions related to the search criteria will follow the programming specifications done in the PSUR 12 for tafamidis.

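### SAP 8.2.6 runs the reproductive-toxicity search on the whole treated set without separating offspring events from the patient's own inherited disease or from paternal exposures

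*Protocol*

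**What the plan says.** - **The search.** SAP 8.2.6, under adverse events and serious adverse events, plans one dedicated table for this risk on the tafamidis treated set. It has an SMQ part, "MedDRA SMQ (Broad and narrow): Congenital, familial and genetic disorders; Foetal disorders; Neonatal disorders, Neonatal exposures via breast milk", and a preferred-term part that includes "Exposure during pregnancy, Exposure via father, Foetal exposure during delivery". Derivations and conventions are deferred to the PSUR 12 programming specifications, which are not reproduced.
- **The set.** SAP 5.3 defines the treated set by enrollment, consent and tafamidis use. Sex, pregnancy and whose event is recorded play no part. Protocol 9.2.1 admits both sexes.
- **The reporting rule.** Protocol 11.6.1 describes exposure during pregnancy in women only, including the case where "the female becomes, or is found to be, pregnant after discontinuing and/or being directly exposed to tafamidis (maternal exposure". It names among the serious outcomes "congenital anomaly [in a live born, a terminated fetus, an intrauterine fetal demise, or a neonatal death".
- **The disease.** Protocol 7.1 states: "The hereditary forms of ATTR amyloidosis are autosomal dominantly inherited diseases". Protocol 11.4.1 gives "Progression/worsening of underlying disease" as an example of an adverse event, and the table in 11.1 has all adverse events, serious or not, entered in the electronic record.
- **Partner pregnancies.** The Amendment 5 entry in Protocol section 5 records that the requirement to report them was removed. The current 11.6.1 is consistent with that.

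**The concern.** The purpose of the table is to show whether tafamidis harms pregnancies, fetuses, neonates or breastfed infants. The search as written cannot tell an event in a child from an event in the treated patient. In most registries that would matter little. Here the study disease, in its hereditary form, is a familial and genetic disorder, and its progression is reportable as an adverse event. A search group with those words in its name, applied unfiltered to the patients' own records, therefore has an obvious route to counting the indication as the risk.

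The paternal term raises a different problem. It puts two exposure routes with different reporting rules into one count: maternal exposure is requested throughout under the current text, while paternal exposure is no longer requested.

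Reproductive, developmental and lactation toxicity is one of the three important potential risks kept in SAP Table 1, and SAP section 2 says this SAP supports the final study report. A reader of that report would take the table's total as the evidence on the risk. If true offspring events are few, a handful of hits of another kind could change the impression it gives.

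**Working it through.** There is no planned figure to reproduce. The SAP says "There are no hypotheses associated with this survey. All analyses will be descriptive", and Protocol 9.5 says "There is no set number of patients who will be enrolled in the survey". The documents give no treated total, no counts by preferred term and no number of pregnancies. The check is to follow each kind of record through the rule as written.

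| Record in the treated set | Enters the table as written? | Evidence on the risk? |
|---|---|---|
| Anomaly in the child of an exposed woman | Yes | Yes |
| Worsening of hereditary ATTR in a treated man or woman, reported as an adverse event and coded to a hereditary or familial term | Yes, if that term is in the SMQ and PSUR 12 does not remove it | No |
| ATTR amyloidosis recorded only as medical history | No, not an adverse event | No |
| Progression in a wild-type patient | Not by this route, as there is no TTR mutation | No |
| Pregnancy in the partner of a treated man | Yes, the term is named | Paternal route only, and not requested since Amendment 5 |

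The second row needs four things to be true:

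1. Progression is reported as an adverse event. Protocol 11.4.1 and 11.1 support this.
2. It is coded to a disease term, not to the presenting symptom. The documents are silent.
3. That term belongs to the SMQ. The documents do not list the SMQ's terms; this is inferred from its name.
4. The PSUR 12 conventions do not remove it. The documents are silent.

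The last row needs no inference, since the paternal term is in the list.

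Let *a* be the offspring or exposed-pregnancy hits, *b* the patient's-own-condition hits and *c* the paternal hits. The planned table shows *a* + *b* + *c*, and the part that does not bear on maternal exposure is (*b* + *c*)/(*a* + *b* + *c*). All three are unknown. The lower limit for *b* is 0 and the upper limit is every treated patient with an adverse event coded to such a term. The documents do not narrow that range.

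**The case against.** The strongest reply is that mis-capture is not shown. It depends on the content of an SMQ and on a PSUR 12 specification that are both outside these documents, and the over-count may be zero. That stands as a limit on size. It does not answer the point about the rule, because the SAP states no filter and a reader of the final report could not tell whether one was applied.

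Second, a broad search is a defensible choice for a rare potential risk, and narrowing it has dangers. Offspring are not enrolled and the documents describe no infant identifier, so a true fetal event may sit under the mother's number. Excluding everything recorded for the patient could lose it. Deleting the paternal term would discard reports collected while they were still required. Both arguments stand, and they are reasons to split the table without cutting the search.

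Third, case-level separation is possible. SAP 8.2.6 also plans an adverse event listing for all enrolled patients and a listing of serious events in the treated set. Protocol 11.6.1 follows exposed pregnancies through a supplemental form and TESPO, with questionnaires at 6 and 12 months after birth. That stands too: the weakness is in the summary table, and the information behind it is not lost.

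A reader might also infer that the SAP contradicts Protocol 11.6.1. It does not. Section 11.6.1 is a rule for reporting to the sponsor and defines no analysis count, and the safety concern in Table 1 is not restricted to maternal exposure.

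**Conclusion.** The point holds as a possibility that the SAP wording leaves open. The only dedicated table for this risk can count the treated patient's own inherited disease as apparent reproductive toxicity, and it pools paternal exposures that are incompletely ascertained after Amendment 5. The first part assumes that at least some progression events were coded to a term in the SMQ and that PSUR 12 does not filter them. The second follows directly from the term list. The size is unknown and may be zero.

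Two stronger readings are tempting and are not supported. One is that the table will be dominated by the study disease, or that the final report could not separate drug effects from inheritance: no counts are given, and the listings and TESPO allow cases to be reviewed. The other is that children who inherit a TTR mutation will swell the count: the documents describe no genotyping of offspring and nowhere treat an inherited allele without disease as an adverse event or anomaly.

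No hypothesis test or decision rule depends on the table. What is affected is how a descriptive table on a retained important potential risk can be read, and that is enough to justify a small change.

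**What to change.** Keep the search terms as they are. In SAP 8.2.6, present the hits on three lines:

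- **(a)** Events in a pregnancy, fetus, neonate or breastfed infant of an exposed woman, including those recorded under the mother's number. This is the line used for the risk.
- **(b)** Congenital, familial or genetic terms that describe the treated patient's own condition, ATTR amyloidosis included. These are shown but not counted toward the risk.
- **(c)** *Exposure via father*, on its own line, with a note that reporting of partner pregnancies was not required after Amendment 5.

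State in the same place any PSUR 12 filter that applies, so that the final report can be read without that specification.

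The cost is a few sentences in the SAP, a line assignment in the table program, and medical review of what should be a small number of hits. Data collection does not change and no hit is discarded.
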